2.4. UH3/Phase 2 Milestones

UH3/Phase 2 Timeline (Years 3-5 of Project).	Quarter
Administrative	
All staff hired and trained	10
Manual of Procedures (MOP) finalized	12
100% compliance with PRISM Program policies and practices, including workgroup participation (Annual)	12, 16, 20

100% compliance with Protocol (Annual)	12, 16, 20
100% compliance with Data and Safety Monitoring Plan (Annual)	12, 16, 20
Investigator Steering Committee meets monthly & project teams meet 1-4X/monthly (Annual)	12, 16, 20
All staff maintain "trained" status each year including required human subjects training (Annual)	12, 16, 20
Results submitted to clinicaltrials.gov	20
Final report submitted	20
UH3 Aim 1: Randomized Trial	
Recruitment and Enrollment	
Study Open to Enrollment	10
50% total sample enrolled (w/ completed baseline) per year (35% female; 35% racial/ethnic minority)	13, 17
Intervention delivery	
50% total sample participate in intervention per year (Annual)	15, 19
75% satisfied with RAMP program	19
75% of intervention participants attend/engage with recommended # of sessions ($\geq 6/9$)	19
15% of intervention sessions fidelity checked and Health Coach Facilitators achieve high fidelity rates ($> 90\%$)	18
Data assessment and retention (Assess all participants at 3- and 6-month timeframes)	
Data collected at 3 and 6 months for 50% of participants per year	15, 19
> 80% of participants each year retained for primary outcome at 6 months	15, 19
Data analysis	
Final dataset transferred to statisticians for data analysis	20
Aim 1 data analysis completed	20
UH3 Aim 2: Implementation Aim	
Meet with patients and community advisors at least 3X/year	12, 16, 20
Meet with VA advisors at least 1X/year.	12, 16, 20
Aim 2a. Conduct mixed-methods assessments of advisor and randomized trial participant views of implementation-related barriers and facilitators, resource needs, and other RE-AIM/PRISM domains	
Aim 2a data collection and data analysis completed	20
Aim 2b. Work with advisors to co-create additional plausible strategies for overcoming barriers to implementation of RAMP in the national VA healthcare system	
Aim 2b process plans and implementation strategies completed	20
Aim 2c: Conduct budget impact analyses using models informed by advisor views to inform future decision making	
Aim 2c budget impact analysis completed	20
Implementation and Dissemination	
Experimental intervention Adaptations	
Necessary intervention adaptations based on results completed	20

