5.1.2 Feasibility/Pilot and RCT

Interventions

RAMP (UG3/Phase 1 Aim 2 and UH3/Phase 2 Aim 1)

Eligible participants will be enrolled in the RAMP intervention group and mailed (by

Abbreviated title: Rural Veterans Applying Mind Body Skill for Pain (RAMP)

Version date: 8/22/25

postal mail) tailored informational materials, including an introductory letter, copy of the information sheet, schedule with meeting dates/times, a workbook, and directions for accessing the intervention materials online. In keeping with our pragmatic approach, participants will not be asked to limit any other treatment. RAMP will take place over a 3-month period, delivered virtually via a VA-approved program (e.g., Microsoft Teams, Webex). For the UG3/Phase 1, the first session was a one-to-one session (60 minutes) with a health coach to complete a Personal Health Plan. This was followed by 11 weekly group sessions (90 minutes each) facilitated by the health coach. For the UH3/Phase 2, revisions were made, and all 9 weekly sessions will be held as a group (90 minutes each) facilitated by the health coach. Videos will be interspersed with workbook reflections and group discussions facilitated by the health coach. In session, group viewing of expert narrated videos will provide consistent education and training in content (e.g., pain education, mind-body skill training like mindfulness, physical movement, wellbeing). A range of customizable options and resources will be provided to meet Veterans' preferences, needs, and abilities. Email, SMS (using Qualtrics FedRAMP), and/or phone communication will provide reminders of sessions ahead of time. Participants will be asked to remain in close contact with health coaches and let them know of any need to miss a session. Study staff will follow-up with participants who do not attend session(s). Additional contact reasons, particularly towards the end of the study, may include alerting participants to study results and other research participation opportunities.

Usual Care (UH3/Phase 2 Aim 1 only)

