Participants randomized to the Usual Care (UC) condition will not be asked to do anything besides complete the follow-up surveys. In keeping with our pragmatic approach, patients will not be asked to limit any other treatment. They will be mailed (by postal mail) an introductory letter, copy of the information sheet, and schedule of when they will be contacted to complete the follow-up surveys. After completing the final follow-up survey, they will be mailed information about how to access the intervention materials online.

Follow-up

Participants will be asked to complete follow-up surveys online at 3 months (UG3/Phase 1 and UH3/Phase 2) and 6 months (UH3/Phase 2 only) after the intervention period began. Survey invitations will be sent via email and SMS (using Qualtrics FedRAMP). Reminders will be sent to non-responders, including phone and mail follow-up if necessary.

All recruitment and follow-up activities will be performed by project staff at the Minneapolis VA.

Participant Population Characteristics

In order to qualify for the US Military, and eventually become a Veteran, individuals must be at least 18 years old. Since children (less than 18 years of age) do not exist in the population of interest, they will not be included in the study. This is also consistent with NIH Policy and Guidelines on the Inclusion of Children as Participants in Research Involving Human Subjects.

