Patients will be required to have an email address in the EHR. We will use the Health Resources & Services Administration (HRSA) defined Rural-Urban Commuting Areas (RUCA) using zip codes to identify rural patients. The Data & Statistics Teams will then assign these patients a Study ID and create a crosswalk so that identifiable data is kept behind the VA firewall. Introductory postcards will be mailed to these patients. Patients will then be sent emails with a link to the study website, which will include information about the study, instructions for accessing the screener survey, an opt-out option, information about monetary incentives (\$25 per survey for the feasibility/pilot; \$40 per survey for the RCT), and the study contact information (phone number and email address to contact for help). We anticipate needing to send postcards and emails to up to 30,000 (about 2,000 during the pilot and about 28,000 during the full RCT) people in order to reach our randomization goals. As of October 2022, there were over 50,000 VA patients in the EHR who meet our initial eligibility criteria. Patients who go to the study website will be encouraged to review an information sheet and general introductory information as well as access the initial screener survey using a unique identifier (Qualtrics FedRAMP ID) via either a secure, unique or shortened URL. If participants screen eligible, they will then continue in Qualtrics FedRAMP to complete the baseline survey. This will be followed by a chart review by specially trained staff who will review VA EHR charts for mental health exclusions (see below). Project staff will call eligible participants to verify eligibility, availability, and interest. They will review information sheet details and provide the opportunity for participants to ask

questions before obtaining verbal consent and proceeding to randomization (UH3/Phase 2 only)/full enrollment (both UG3/Phase 1 and UH3/Phase 2).

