Our power calculation uses the Brief Pain Inventory (BPI) interference scores over the entire follow-up period as the primary outcome measure. The primary outcome uses a repeated measures approach that takes into account assessments at 3 and 6 months with a single test of significance. Secondary outcomes will evaluate the time points separately. For our primary analysis we estimate up to 20% attrition, so at least 500 people will need to be randomized to obtain a sample of 400 people with complete data. 200 participants in each arm will yield 90% power, with an alpha of 0.05, to reject the null hypothesis of equal means over the repeated follow-up time points (i.e., 3 and 6 months) if the arms differ by an effect size of 0.3 or greater. This includes a conservative estimate that the repeated outcome measures are highly correlated ($r=0.7$) and even with only 1 time point there is power to detect effect sizes of 0.32. Analyses that are stratified by subgroups as small as 70 people per arm (i.e., equivalent to restricting to only women or minority Veterans) would have approximately 90% power to detect differences of 0.50. However, these would only be exploratory in nature and not adjusted for multiple comparisons. While our goal is to achieve 500 randomized participants, our intervention will roll out in large waves so precisely hitting a randomized sample number is difficult. Therefore, we asked for an administrative IRB approval to exceed this goal and enroll up to 550 participants.

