We will use an intention-to-treat approach. Preliminary descriptive analyses will summarize the distributions of the baseline measures across treatment arms overall and will similarly assess the outcome distributions across assessment time points (i.e., baseline, 3, and 6 months). We will summarize the completeness of the self-reported outcome assessments and examine associations between completeness and baseline measures as well as the association with secondary outcome assessments that are collected from the electronic medical record (e.g., medications, health care utilization related to pain treatment). Initial analyses will use all available follow-up data and subsequent sensitivity analyses will examine the potential effect of response bias. For analyses of the primary outcome, all repeated measurements of the BPI interference score will be fitted in a mixed model for repeated measures as a function of the group assignment, while controlling for time points and baseline values of the outcome as fixed effects, with participants as random effects. Between-group differences over the entire follow-up period (average of 3 and 6 months) will be the primary test of treatment group differences. Between-group differences will be estimated for each of the individual time points as secondary outcomes. Similar to the methods described above for the primary analyses, weighted selection model analyses will examine the sensitivity of the initial results to response biases. To do this, we will fit a series of weighted selection model analyses. Each analysis will use an expectation-maximization algorithm to estimate weights to assign to potential values of the missing outcomes for use in the regression model. The secondary outcomes will be similarly analyzed

using the same linear mixed effect models for normal continuous measures and appropriate generalized linear mixed effect models for non-normal measures.

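### RAMP is delivered in coach-led groups and Usual Care is not, but the analysis models have only a participant random effect; if shared delivery correlates outcomes within RAMP groups, the planned test's alpha is above 5%.

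*Combined protocol and SAP*

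**What the plan says.** **Delivery.** Section 5.1.2 says of the RCT version of RAMP that "all 9 weekly sessions will be held as a group (90 minutes each) facilitated by the health coach". Of the control arm it says: "Participants randomized to the Usual Care (UC) condition will not be asked to do anything besides complete the follow-up surveys".

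**Randomisation.** Section 5.2.2 describes a call to each eligible person, in which staff answer questions "before obtaining verbal consent and proceeding to randomization (UH3/Phase 2 only"). Individual randomisation is the natural reading, though the unit is not stated outright.

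**Model.** Section 5.8 fits the repeated BPI interference scores as a function of arm, "controlling for time points and baseline values of the outcome as fixed effects, with participants as random effects". The primary test is the between-arm difference averaged over 3 and 6 months. "The secondary outcomes will be similarly analyzed", with the same linear mixed models for normal measures and generalised mixed models for others.

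**Power.** Section 5.8 and DSMP 7.2 state that "200 participants in each arm will yield 90% power, with an alpha of 0.05", for an effect size of 0.3. The only correlation mentioned is the within-person value of 0.7.

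No section supplied gives a session-group size, an ICC, a design effect, a group or coach term, or a cluster-robust standard error. The planned sensitivity analyses concern response bias only.

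**The concern.** This is a partially nested design: one arm is treated in groups and the other is not. Members of a RAMP group share a coach, a discussion and a set of peers. If that sharing moves their outcomes together, the RAMP arm holds less independent information than its headcount suggests. A model whose only random effect is the participant cannot see this. It then reports a standard error for the arm difference that is too small, and the single confirmatory test rejects too often. The linear secondary models inherit the problem directly. For the generalised models it is inferred from the statement that they follow the primary approach.

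The remedy depends on a variable that has to be linked to each participant. It also adds a variance term that should be fixed before results are seen.

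**Working it through.** **Inputs from the documents** (5.8, DSMP 7.2): 200 analysed per arm, effect 0.3 SD, within-person correlation 0.7, alpha 0.05.

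**Assumptions:** m = 8 to 15 analysed members per RAMP group. ICC = 0.01 to 0.05 among assigned RAMP members, as a share of the variance of the two-visit mean. RAMP groups are treated as a sample of the groups that could be run.

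**1. Reproduce the stated power.** The SD of the two-visit mean is sqrt((1 + 0.7)/2) = 0.922. The standard error is 0.922 × sqrt(2/200) = 0.0922, and 0.3/0.0922 = 3.254. Power is Φ(3.254 − 1.960) = 0.902. The stated 90% reproduces with a two-sided test and independent participants.

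**2. Add correlation in the RAMP arm only.** The true variance of the difference is (σ²/n)[2 + (m − 1)ICC]. The planned model uses 2σ²/n. The ratio is f = 1 + (m − 1)ICC/2, and the actual alpha is 2[1 − Φ(1.960/√f)]. For m = 10 and ICC 0.03, f = 1 + 9 × 0.03/2 = 1.135, √f = 1.065, 1.960/1.065 = 1.840 and alpha = 0.066. The planned standard error is about 6% too small.

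| m | ICC | f | Planned-test alpha | Group-aware power at 0.3 SD (normal formula) |
|---|---|---|---|---|
| 8 | 0.01 | 1.035 | 0.054 | 0.892 |
| 8 | 0.03 | 1.105 | 0.062 | 0.872 |
| 10 | 0.03 | 1.135 | 0.066 | 0.863 |
| 10 | 0.05 | 1.225 | 0.077 | 0.837 |
| 15 | 0.03 | 1.210 | 0.075 | 0.841 |
| 15 | 0.05 | 1.350 | 0.092 | 0.800 |

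**3. Simulation check** (complete data, 20 groups of 10, 200 per arm). Planned-test alpha is 0.050 with no group effect, 0.064 at ICC 0.03 and 0.073 at ICC 0.05. A Satterthwaite comparison of RAMP group means with Usual Care individuals gives 0.049 at ICC 0.03.

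**4. Baseline adjustment.** If the ICC is a share of the baseline-adjusted variance, f and alpha are unchanged. If it is a share of the unadjusted variance and baseline correlates 0.5 with the two-visit mean (assumption), f = 1 + (m − 1)ICC/[2(1 − 0.25)] and alpha runs from 0.055 to 0.106 (0.071 at m = 10, ICC 0.03).

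**5. Non-attendance.** The milestone is that "75% of intervention participants attend/engage with recommended # of sessions". If only 75% share the group effect (assumption), an ICC of 0.05 among them becomes 0.75² × 0.05 = 0.028 among all assigned, and alpha at m = 10 is 0.065.

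**6. Power with small-sample degrees of freedom.** The last column of the table omits them. Simulated with Satterthwaite degrees of freedom, power is about 0.85 at m = 10, ICC 0.03, and about 0.77 with 13 groups of 15 at ICC 0.05. Without baseline credit the range is therefore about 0.89 down to 0.77. With the 0.5 baseline correlation and the ICC on unadjusted variance, the normal formula gives 0.96 down to 0.87.

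**7. Correlation that does not inflate alpha.** If the correlation comes only from how individually randomised people are sorted into groups (ICC about 0.03), the planned test's alpha is 0.052 and the grouped test's is 0.038. If it comes only from waves shared by both arms (20 groups of 10 in 5 waves), the planned test stays just under 0.05. A RAMP-only group term without a wave term drops to about 0.04 at wave ICC 0.03 and about 0.03 at wave ICC 0.05.

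**8. Enrolling 550.** This gives 550 × 0.8/2 = 220 analysed per arm. Because f does not contain n, alpha at m = 10, ICC 0.03 stays at 0.066, and group-aware power is 0.893.

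**The case against.** The strongest reply is that the ICC may be very small. Content comes from the same expert-narrated videos in every group (5.1.2). Facilitators use standardised checklists, and 15% of sessions are assessed against a 90% delivery goal (DSMP 7). The programme lasts 9 weeks, so the 6-month outcome is measured well after groups end. This stands as a reason to expect the lower part of the range. It does not make the ICC zero, because facilitated discussion and group dynamics remain, and the plan does not argue that they are negligible.

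A second reply is that the inflated alpha belongs to a particular null: a zero average effect with group effects that differ. At ICC 0.05 the between-group SD is sqrt(0.05) × 0.922 = 0.21 single-visit SD, so about 17% of groups would end more than 0.2 SD worse, offset by others doing better. That is correct. If RAMP changes nobody's outcome, alpha stays at 5%.

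A third reply concerns the remedy. Section 5.8 says the intervention rolls out in large waves. A RAMP-only group term without a wave term would count variance common to both arms as delivery variance and be too conservative. This also stands, and the fix includes wave for that reason.

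A reader might go further and infer that the trial's type I error is in fact 7% to 9%, or that the trial is underpowered and must enrol more. The documents support neither. They give no group size or ICC, and the power statement takes no credit for the baseline adjustment that the model already contains.

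**Conclusion.** The concern holds in conditional form. The plan omits any allowance for correlation within RAMP session groups, and with any positive delivery-induced ICC the planned test's alpha is above 5%. Under the assumed 8 to 15 analysed members per group and ICC 0.01 to 0.05, alpha is about 0.054 to 0.092, and the programme's standardisation favours the lower part of that range. The direction is certain given the condition; the size is not documented. It also rests on individual randomisation, which is inferred.

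Power is the lesser point. A group-aware model costs some power, and the planned baseline adjustment may recover it, so 90% is not assured but is not shown to be missed. The permission by which "we asked for an administrative IRB approval to exceed this goal and enroll up to 550 participants" does not bear on alpha. This should be fixed because it affects the only primary test and is cheap to correct before analysis.

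**What to change.** - **Data.** Record each RAMP participant's session group. Session schedules and attendance are already kept, so this should add little work.
- **Model (5.8).** For primary and secondary outcomes, add a random effect for session group in the RAMP arm only, with Usual Care participants as singletons. Use Satterthwaite or Kenward-Roger degrees of freedom for the linear models. Include randomisation wave as a fixed effect in both arms, so that variance the arms share is not counted as delivery variance.
- **Power (5.8 and DSMP 7.2).** Restate power or the detectable effect for the planned group size over a stated ICC range, using the same small-sample degrees of freedom. Say which variance the ICC refers to and what baseline correlation, if any, is credited. Keep n = 500.
- **Masking.** Session group reveals arm, whereas DSMP 8.4.1 keeps allocation masked until the study statistician's analysis is complete. Fix and date the model code before session group is linked, and reconcile 8.4.1 with that step.

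**Cost:** wording in three sections and one recorded variable. Stated power is slightly less favourable if no baseline credit is taken. The test is mildly conservative if the correlation comes only from sorting (simulated alpha 0.038 at ICC about 0.03).

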6.0 Reporting

6.1 Minneapolis VA

We will follow the Minneapolis VA IRB reporting requirements for all issues that must be reported (i.e., unanticipated serious adverse events (U-SAEs), unanticipated problems (UAPs), protocol deviations/violations/noncompliance, and any changes with respect to the protocol). The project staff will remain in regular contact (by phone, email, videoconference, and face-to-face) to discuss study processes, progress, and any issues encountered. Any issues will be reported directly to the MPIs. Data will be reviewed regularly to ensure accuracy and data

privacy. In the case of problems, the project director will immediately discuss with the study MPIs. MPI [name] will report any related or possibly related U-SAEs or Deaths to the Minneapolis IRB within 5 business days of learning of the event(s). If there are modifications or amendments to the study MPI [name] will also complete the appropriate forms and wait for approval prior to implementation. As described below, IRB notification forms will be completed to notify Data and Safety Monitoring Board (DSMB) of findings.

6.2 NIH

In addition, as guided by the NIH's policy on data and safety monitoring, a detailed data and safety monitoring plan (DSMP) was developed and submitted to NIH program officials for approval prior to data collection. See Appendix A for current DSMP. The DSMP aims to ensure the safety of participants and the validity and integrity of the data collected. A Manual of Operations is also being developed, including standard procedures for protection of all subjects and data collected from participants in both hardcopy and electronic formats, from the point of collection to storage.

NIH advised the project team that a Data and Safety Monitoring Board (DSMB) is required for the UG3/Phase 1 and UH3/Phase 2 of the project. The number of members and specific areas of content expertise for an appointed DSMB was agreed upon with NIH prior to funding. Safety and other data outlined in the DSMP (Appendix A) will be monitored by the MPIs on a monthly basis. The DSMB establishes the frequency of monitoring in the charter agreed upon by the board.

6.2.1 Framework and information monitored

The following information will be collected and monitored as part of the DSMP: participant flow (as per CONSORT recommendations); enrollment; allocation; data collection; findings from quality assurance and quality control procedures; safety (including adverse events described below and in Appendix A); and protocol deviations. No interim analyses are planned given the low expected risks with the study.

6.2.2 Adverse Event Monitoring

We will monitor and report adverse events and unanticipated problems involving risk to subjects or others (UPIRTSO) to our local IRB, DSMB, and the funding agency as required. Active and passive surveillance methods will be used to monitor for adverse events. We will ask about potential adverse events at all study visits and data collection events. Participants will also be asked to notify study personnel (outside of scheduled sessions and reporting) about serious adverse events that occur. Trained project staff will be responsible for documenting adverse events and notifying the principal investigators. The MPIs will have final determination regarding the classification and reporting of adverse events to applicable regulatory bodies (e.g., IRB, DSMB, funding agency). The MPIs will report serious adverse events and unanticipated problems to the appropriate regulatory bodies within 5 business days or other required amount of time.

